10.0 Sharing of Results with Subjects

10.1 *Describe whether you will share results (study results or individual subject results, such as results of investigational diagnostic tests, genetic tests, or incidental findings) with subjects or others (e.g., the subject's primary care physician). If so, describe how you will share the results and include this information as part of the consent document. Upload materials you will use to explain the results to subjects:*

At the conclusion of the study or when the participants' involvement in the study ends, interested participants will be provided with individual results related to their body composition, BMD, fitness, and pertinent blood markers. These data will be summarized on a TBD summary document that the participant can pick up at the lab or have (upon request) mailed to them at a provided address. This form will be submitted as an Addendum before it is provided to the first participant. Participants will only be provided results during the study if it is determined that the participant has a result for any measured outcomes that is out of the normal range; in this case the participant would be provided information about the value and asked to see their personal health care provider. The participants will also be notified when a summary of the study findings is published if an active email address is on file.

11.0 Study Timelines

11.1 Describe:

- *The duration of an individual subject's participation in the study (for example, 1 hour, 2-4 weeks, 3-5 years).*
- *The amount of time expected to enroll all study subjects (weeks, months, years, etc.)*
- *The amount of time expected for the investigators to complete this study including primary data analyses.*

The duration of an individual's participation in this study will be approximately 6 to 10 weeks, which will include a Zoom or telephone call for screening, a screening visit in the laboratory, a baseline visit, three days of habitual diet and exercise tracking, two experimental conditions, and a washout period of 1 menstrual cycle (approximately 3 weeks). The actual time and frequency of the subject's visits will depend on their schedule and that of the study staff. Participants will begin the study on a rolling basis, but the entire study will take place across approximately 6 months based on enrollment of 1-2 participants per week. The investigators will complete primary data analyses within the following year but all analyses of study data may not occur for up to ten years following study completion.

12.0 Inclusion and Exclusion Criteria

12.1 Describe how you will screen individuals for eligibility. When will screening occur and what procedures will you use? Upload any screening scripts or surveys to Protocol Management:

Those who respond to the investigation's advertisements will be asked to complete a brief telephone (or Zoom) screening to confirm basic eligibility criteria. Participants will be made fully aware of the eligibility criteria, time commitment, possible risks and their right to withdraw from the study at any time. A phone screening form will be used for this purpose conducted by a research team member who is also a registered dietitian nutritionist (RDN). The Low Energy Availability in Females Questionnaire will be used to screen for risk of existing LEA, medication use, menstrual function, and injury history.

12.2 Describe the eligibility criteria that define who will be included and who will be excluded from enrollment for each procedure of your study.

Include any geographic criteria (e.g., Virginia Tech undergraduate students, a national sample of adults with engineering degrees, minors aged 8-12 in the New River Valley, university faculty in Virginia and Paris, France):

Eligible participants will be well-trained, eumenorrheic female runners between the ages of 18-35 years that are weight-stable with a BMI between 18.5-30 kg/m². Participants with LEAF-Q scores ≥ 8 , existing menstrual disturbances measured by progesterone and self-report, or low BMD (z-score <-2) will be excluded from the study to prevent worsening existing conditions and recommended to follow up with their primary care physician and/or a registered dietitian nutritionist. During the phone screening, participants will be asked if they have ever been diagnosed with an eating disorder and the circumstances surrounding the diagnosis. If the participant has just recently recovered (within the last 12 months) or is still in recovery, she will be excluded from the study. The LEAF-Q was not developed to assess disordered eating behavior, however, a study in ultra-marathon female runners found a significant association between high LEAF-Q scores and disordered eating (Folscher, Grant et al. 2015). Athletes who score 8 or higher on the LEAF-Q will be excluded from the study and referred to a local sports dietitian. Participants using contraceptives (oral contraceptives, injections, IUD, etc.) will be excluded from this study. Contraceptive use may mask menstrual irregularities and oral contraceptives may influence glucose metabolism (Lopez, Schultz 2007), a secondary outcome of this study. Adequate training status for the study protocol will be assessed based on running volume, frequency, and VO₂max. Eligible participants must be able to run on 5 days/week for at least 60 minutes to meet the training requirements of the study protocol. Additional exclusion criteria include history of fracture in previous 6 months, medication use that could potentially affect bone metabolism (e.g., corticosteroids, anticonvulsants, heparin, gonadotropin-releasing hormone agonists), pregnancy, lactation, abnormal TSH, and routine engagement in mechanical loading exercises. Participants must be willing to consume the diets provided, however, diets will be modified based on patient allergies or preferences, within reason. Participants will be excluded if they have dietary restrictions or preferences that would prevent them from consuming meals that fit within the experimental conditions. For example, we cannot modify diets to meet low-carbohydrate preferences given the experimental diets must contain 55% of total calories from carbohydrates. Similarly, participants who are unable to consume high-fiber diets will be excluded.

12.3 Indicate specifically whether you will include or exclude each of the following special populations: (You may not include members of these populations as subjects in your research unless you indicate them in the description of your subject population.)

- *Minors, as defined by state law where the study is performed (infants, children, teenagers)*
- *Pregnant women (can be included in minimal risk studies by mentioning in section 13.1)*
- *Prisoners (including all incarcerated individuals)*
- *Adults not capable to consent on their own behalf*

None of the above will participate.

Pregnant women are excluded because intentional energy restriction is not appropriate during pregnancy. A pregnancy test will be performed at baseline prior to the DXA scan and after the 3-week washout period on Day 1 of the second experimental condition.

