adolescence and bone formation in adulthood, leading to an elevated risk of fracture and osteoporosis later in life (Papageorgiou, Dolan et al. 2018).

The recommended treatment for LEA is to increase energy availability to optimal levels (45 kcal/kgFFM/d) by increasing EI, decreasing EEE, or a combination of the two (Kuikman, Mountjoy et al. 2021). However, inadequate energy is not always intentional as in the cases of disordered eating/eating disorders and “cutting weight”. Some athletes may experience LEA unintentionally due to factors such as inadequate knowledge of fueling recommendations, decreased appetite, lack of time, or low food security (Wasserfurth, Palmowski et al. 2020). Therefore, not all athletes may be willing or able to achieve optimal energy availability. Given the significant risk to long-term bone health, strategies to counteract the effects of LEA on bone metabolism are necessary.

Compared to inactive controls, runners on average have higher BMD and bone strength (Scofield, Hecht et al. 2012). However, lower total and site-specific BMD has been reported in female endurance runners compared to sprinters and athletes competing in higher impact sports (Tenforde, Carlson et al. 2018, Mudd, Fornetti et al. 2007). Lower BMD in this population may partially be attributed to a high prevalence of LEA and risk of disordered eating (DE) and clinical eating disorders (EDs) among female and endurance athletes (Melin, Tornberg et al. 2015). Mechanical loading through weight-bearing exercises, such as high-impact loading activities and resistance training, provides an osteogenic stimulus and non-pharmacological approach to improving bone health (Hart, Nimphius et al. 2017, Beck, Daly et al. 2017). In a cross-sectional study of male distance runners, BMD was found to be significantly higher in runners who reported routine engagement in resistance training compared to runners who did not weight train and untrained controls (Duplanty, Levitt et al. 2018).

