Health History: Subjects will be asked to complete a standard health/medical history questionnaire, which will be used to screen for health issues (e.g., coronary or congenital heart disease) or other reasons (medications which influence study results) that would preclude participation (see uploaded Health History Screening Questionnaire). This questionnaire has been used by [name] for clinical studies for the past 17 years.

Low Energy Availability in Females Questionnaire (LEAF-Q): Subjects will be asked to complete the LEAF-Q, which will be used to screen for risk of existing LEA, medication use, menstrual function, and injury history. The LEAF-Q has been validated as a screening tool for LEA in female endurance athletes (Melin, Tornberg et al. 2014). Individuals who score as "high risk" for LEA will be provided referral information to a local sports dietitian.

Body Weight Height and Composition: Body weight and height will be measured on a digital physician's scale. Percent body fat and fat-free mass will be measured in all subjects via DXA scan.

Bone Mineral Density: Total body, dual-femur, and lumbar spine BMD will be measured in all subjects via DXA scan. Scans will be conducted by [name] who is an ISCD Certified Bone Density Technologist.

Urine sample and pregnancy test: All participants will be required to provide a small cup of urine immediately before the DXA at baseline. The urine will be evaluated for hydration status via specific density using a refractometer. A pregnancy test will be performed on the urine sample for all participants.

Baseline Laboratory Testing Session (approximately 1 hour).

22-168 The Effect of Impact Loading on Bone Biomarkers in Energy-Restricted Female Runners

All measurements will be performed in the morning after a 12-hour fast (no caffeine) with the participants instructed not to engage in heavy exercise for 36 hours prior to testing and to adequately hydrate the evening prior.

Blood Draw: Blood will be drawn by venipuncture after a 12-hr fast (no caffeine) for the following: CBC, TSH, and progesterone. In total, blood will be drawn five times during the study by venipuncture from a vein in the arm. These include baseline, and the days immediately before and after each experimental condition as explained below. Blood will be drawn with the participant seated quietly in a phlebotomy chair. Approximately 10 ml will be obtained during the baseline visit.

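### Section 12.2 screens for eating disorders only through a self-reported diagnosis, so a woman with an undiagnosed disorder who passes the indirect filters would enter both energy-restricted conditions

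*Combined protocol and SAP*

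**What the plan says.** Section 12.2 contains one criterion on eating disorders. At the phone screen, "participants will be asked if they have ever been diagnosed with an eating disorder and the circumstances surrounding the diagnosis". The rule attached to the answer is: "If the participant has just recently recovered (within the last 12 months) or is still in recovery, she will be excluded from the study".

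The same paragraph then turns to the LEAF-Q: "The LEAF-Q was not developed to assess disordered eating behavior, however, a study in ultra-marathon female runners found a significant association" between high scores and disordered eating. The rule that follows is: "Athletes who score 8 or higher on the LEAF-Q will be excluded from the study and referred to a local sports dietitian". Section 8.2 describes the LEAF-Q as a tool "which will be used to screen for risk of existing LEA, medication use, menstrual function, and injury history", and Section 12.1 gives the same four purposes. Eating disorders are not among them.

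One other screening form is described, in Section 8.2: "Subjects will be asked to complete a standard health/medical history questionnaire, which will be used to screen for health issues". Its items are not reproduced. Section 25.1 refers to an uploaded phone screening form, which is not reproduced either.

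On the population, the rationale in Section 3.3 partly attributes lower bone density in female endurance runners to "risk of disordered eating (DE) and clinical eating disorders (EDs) among female and endurance athletes", together with a high prevalence of low energy availability.

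**The concern.** The criterion depends on a diagnosis having been made and disclosed. A woman who has never been diagnosed can truthfully answer no, and the rule on recovery then never applies to her. A woman with a diagnosed, active disorder who is not in recovery falls outside the literal wording, although it is clearly not meant to admit her.

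What is at stake is participant safety. The intervention is deliberate energy restriction, given twice. Sections 8.3 and 17.1 themselves list mood disturbance and psychological burden among its risks. Sections 8.3 and 12.2 justify excluding women with menstrual disturbance, existing low energy availability or low bone density on the ground that restriction could aggravate a condition already present. The same reasoning applies to an undetected eating disorder, yet the plan describes no direct check for one.

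**Working it through.** No sample-size or error-rate arithmetic applies. The check is to follow one hypothetical woman, with an active but never-diagnosed disorder, through each filter in the plan.

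| Filter | Where | What it can detect | Can she pass? |
|---|---|---|---|
| Phone question on diagnosis | 12.2 | A diagnosis, past or current, that is disclosed | Yes, by answering truthfully |
| Recovery rule | 12.2 | Recovery within 12 months or still under way | Yes, it is not reached |
| LEAF-Q of 8 or more | 8.2, 12.2 | Risk of existing low energy availability; the plan cites an association with disordered eating | Yes, if she scores below 8 |
| Menstrual disturbance | 12.2 | Low progesterone or self-reported irregularity | Yes, if she is cycling normally |
| Weight stability, BMI 18.5-30 | 12.2 | Weight change, low or high BMI | Yes, if within range |
| BMD z-score below -2 | 12.2 | Low bone density | Yes, if not below -2 |
| TSH | 12.2 | Thyroid abnormality | Yes, if normal |
| Willingness to eat the study diets | 12.2 | Incompatible restrictions or preferences | Yes, if she accepts the menus |
| Health history form | 8.2 | Not shown | Cannot be determined |
| Phone screening form | 25.1 | Not shown, beyond the topics named in the text | Cannot be determined |
| Three-day food records | 8.2 | Habitual intake | Yes, no exclusion rule is attached |

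No eating-disorder instrument, symptom question or interview appears in the procedures of Section 8.2 or in Table 1. Such a woman therefore meets no exclusion that the text sets out.

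**What she would be exposed to.** Intake is 30 kcal/kgFFM/d and the exercise target is 15 kcal/kgFFM, so energy availability is 30 - 15 = 15 kcal/kgFFM/d, the value stated in Section 17.2. Section 14.4 has every enrolled participant complete both conditions, so this runs for 2 x 5 = 10 days in total.

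**What would catch her later.** The safety endpoints in Section 4.2 cover excess weight loss, glucose change, soreness, fainting, injury and fatigue. The monitored data in Section 21.1 are of the same kind. Neither includes an item on eating behaviour, so screening is the main protection against this particular risk.

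**What was intended.** The version 2 entry in the amendment history describes the exclusion as covering a recent or current eating disorder. The difference from the present wording is not counted as an error. It does show that naming a current disorder would not change policy.

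**Size.** An estimate would need the prevalence of undiagnosed disorder among women who pass all the filters above, which in turn depends on how well the LEAF-Q and the unseen forms detect it. The documents give none of these.

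**The case against.** The best defence is that the plan has more protection than its one eating-disorder sentence suggests. The phone question asks about any diagnosis ever made and about its circumstances, so it reaches current diagnoses, and a registered dietitian asks it. The LEAF-Q concession is followed at once by a cited association with disordered eating, which is the plan's reason for treating a score of 8 or more as a firm exclusion with referral. The menstrual, bone-density, BMI and weight criteria each remove some women whose eating is disordered. Exposure is limited to two 5-day blocks, with laboratory visits on 7 consecutive days, daily weighing that is not shared with the participant, and a weight-loss safety endpoint of 5 lb.

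All of this stands as mitigation. It does not close the gap. An association in one ultra-marathon cohort does not show that a score below 8 rules out a disorder, and the remaining filters measure physical consequences that need not be present.

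Two stronger readings should be resisted. A reader might infer that the plan knowingly admits women with an active, diagnosed disorder. The documents do not support that: someone still ill is no further along than someone in recovery, and the amendment history confirms the intent, so the wording only needs clarifying. A reader might also infer that eating symptoms are asked about nowhere. That cannot be shown while the health history and phone screening forms are unseen. The claim is limited to the text and Table 1.

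**Conclusion.** The point holds as a specific and inexpensive safety improvement to eligibility. As written, exclusion for an eating disorder depends on a self-reported diagnosis, with the LEAF-Q as an indirect backstop, and an undiagnosed case can pass every criterion the text sets out. This assumes that the two unseen forms contain no eating-disorder symptom items with an exclusion rule attached. If they do, what remains is to describe them in Section 12.2 and clarify the sentence.

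No number can be put on the women affected. Any percentage for the 20 to be enrolled would rest on a prevalence that the documents do not supply.

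A reader might also infer that an undetected case would blur an energy-availability contrast and so bias the trial's comparison. The documents do not support that. RUN and RUN+IL share the same diet and the same expenditure target. Each woman is her own control, with blood drawn before and after each condition. The documents also give no ground for expecting such women to eat less than the diet provided. Section 8.1 collects packaging and uneaten food, Section 8.2 adds a mealtime log, and Section 16.1 allows withdrawal for not eating the diets. The case for change rests on participant protection, not on the validity of the comparison.

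**What to change.** 1. Reword the exclusion in Section 12.2 so that it names a current eating disorder, whether reported or detected at screening, as well as one within the last 12 months.
2. Add a short validated self-report eating-disorder screen, given with the LEAF-Q at the screening visit, and list it in Section 8.2 and Table 1. State the instrument and its cut-off in advance, and handle a positive screen for eligibility as a high LEAF-Q score is handled.
3. If the health history or phone screening form already contains relevant items, say so in Section 12.2 and state what answer excludes.

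The cost is one sentence, one table row and a short form at a visit that already uses questionnaires. The downside is probably a few more screen failures, against the 50-60 women whom Section 14.3 expects to screen in order to complete 12. The diet, exercise, endpoints and analysis are unchanged.

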13.0 Vulnerable Populations

13.1 If the research involves individuals who are vulnerable to coercion or undue influence, please describe additional safeguards you will include to protect their rights and welfare. Consider the applicable items listed below:

- *If the research involves Virginia Tech students, indicate whether these are students of any of the investigators. If so, describe whether the activities will take place during class time as part of the curriculum and the steps you will take to reduce the possibility that students feel obliged to participate in order to improve their course grade. The HRPP can provide further guidance as needed. Describe whether you will request access to student records (e.g., SAT, GPA, GRE scores).*
- *If the research involves employees of Virginia Tech or the research sponsor, describe steps you will take to ensure that the employees are freely participating and describe how their data will be protected from inspection by their supervisors.*
- *If the research involves Virginia Tech NCAA athletes, you must obtain approval from the athletic department.*
- *For research involving Montgomery County Public Schools, you must obtain county approval (after obtaining contingent Virginia Tech approval). Other locales have different requirements; please check on these and describe here. Approval is typically granted by the superintendent, principal, and classroom teacher (in that order). Approval by an individual teacher is insufficient. School approval, in the form of a letter or a memorandum should be uploaded as a supporting document.*
- *If the research involves pregnant women, review “CHECKLIST: Pregnant Women (HRP-412)” to ensure that you have provided sufficient information in this protocol.*
- *If the research involves prisoners, review “CHECKLIST: Prisoners (HRP-415)” to ensure that you have provided sufficient information in this protocol.*

- *If the research involves persons who have not attained the legal age for consent to treatments or procedures involved in the research (minors), review the “CHECKLIST: Minors (HRP-416)” to ensure that you have provided sufficient information in this protocol.*
- *If the research involves cognitively impaired adults, review “CHECKLIST: Cognitively Impaired Adults (HRP-417)” to ensure that you have provided sufficient information in this protocol.*

This research study has the potential to include students and employees of Virginia Tech. However, during the consenting process, the participants will be made aware that only members of the research study team will have access to their data and that this data will utilize a coding system making their data unidentifiable. This data will be locked away and they will be made fully aware of their right to withdraw from the study at any time. If Virginia Tech athletes are interested in the study, they will only be allowed to participate during their off-season and after first obtaining approval from the athletics department.

14.0 Number of Subjects

14.1 *Indicate the total number of subjects to be enrolled and how this number was determined (e.g., sample size calculation [show], number of available subjects in a finite pool, number of tests funding award would allow):*

A power analysis determined that 12 women will be required to detect a clinically significant change of 10 μ g/L in PINP with 80% power at $P < 0.05$ based on results from a similar study of LEA during dietary restriction (Papageorgiou, Martin et al. 2018). We aim to enroll 20 participants to account for possible dropout.

14.2 *If this is a multi-site study, indicate the number of subjects to be enrolled at this site and the total to be enrolled from all sites:*

N/A

14.3 *If applicable, indicate the number of potential subjects you expect to screen for enrollment, and the number of subjects you will need to complete the research procedures:*

We anticipate that we may need to screen between 50-60 participants to recruit and complete the required 12 participants.

14.4 If the study has more than one procedure, indicate the total number of subjects to undergo each procedure separately:

All enrolled participants will undergo the two experimental procedures.

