2.0 Objectives

2.1 *Describe the purpose, specific aims, or objectives of this study:*

- 1) Determine the effect of short-term, high-impact loading on biomarkers of bone remodeling in energy-restricted, female long-distance runners.
- 2) Examine the relationship between undercarboxylated osteocalcin and impact loading on glucose metabolism during acute low energy availability.

2.2 *State the hypotheses to be tested:*

The addition of 50 high-intensity impact loading jumping exercises per day to usual run training will result in less suppression of bone formation following 5 days of endurance running in an energy-restricted condition compared to daily running in an energy-restricted state without high-impact loading exercises.

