serum N-terminal pro-peptide of type 1 collagen (P1NP), a marker of bone formation, and IGF-1 decreased by 15% and 17%, respectively, after 3 consecutive days of treadmill running with energy intake restricted to 50% of estimated needs (Zanker and Swaine 2000). In a more recent cross-over design study (Papageorgiou, Elliott-Sale et al. 2017), changes bone biomarkers were measured in 11 women and 11 men in response to 5 days of daily running under optimal EA conditions (45 kcal/kgFFM/d) and 5 days of daily running under low EA conditions (15 kcal/kgFFM/d). In both conditions, participants ran on a treadmill until an energy expenditure of 15 kcal/kgFFM was achieved. Diets provided 60 kcal/kgFFM/d and 30 kcal/kgFFM/d for the optimal and low EA conditions, respectively. In the female participants, P1NP was significantly lower after the low EA condition compared to optimal EA. Additionally, β -carboxyl-terminal cross-linked telopeptide of type 1 procollagen (β -CTX), a marker of bone resorption, increased 19% in response to the low EA condition and this increase was significantly different from the change in β -CTX observed in the optimal EA condition. No significant change in P1NP or β -CTX were observed in men. This suggests women may be more sensitive to the effects of LEA on bone metabolism and, therefore, be at greater risk. In another cross-over design study of 10 female runners, changes in P1NP and β -CTX were measured after completion of three, 3-day experimental conditions: optimal EA (45 kcal/kgFFM/d), LEA achieved through dietary restriction only (15 kcal/kgFFM/d), and LEA achieved through a combination of dietary restriction and daily running (15 kcal/kgFFM/d) (Papageorgiou, Martin et al. 2018). In the combined diet and exercise LEA condition, participants received diets providing 30 kcal/kgFFM/d and expended 15 kcal/kgFFM/d during a treadmill run. This study found P1NP was significantly reduced after 3 days of LEA achieved through diet only, but not after the combined LEA condition with running. These findings suggest the negative effects of LEA on bone metabolism may be counteracted or masked by the osteogenic effects of weight-bearing exercise, such as running. There were no significant changes observed in β -CTX in response to either LEA condition. Based on these short-term studies, it appears suppression of bone formation occurs before measurable increases in bone resorption. Additionally, the severity of bone impairments may depend on the degree of energy restriction given the dose-response relationship observed between LEA and select bone turnover markers in exercising women (Ihle and Loucks 2004).

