
Benefit of High-Impact Loading on Bone Metabolism. High-impact loading exercises such as jumping, bounding, and plyometric training place a high level of mechanical strain on bone and can elicit osteogenic adaptations (Hutson, O'Donnell et al. 2021). There have been a limited number of studies showing mixed results on the short-term effects of high-impact loading on bone biomarkers (Rantalainen, Heinonen et al. 2009, Rogers, Dawson et al. 2011). Additionally, very few studies have included energy intake assessments and most studies have been conducted in non-athletes. In one study of 26 female non-athletes, markers of bone formation (osteocalcin and bone specific alkaline phosphatase (BAP)) and bone resorption (tartrate-resistant acid phosphatase (TRAP5b) and CTX) were measured in response to either a control condition or jumping intervention (Kishimoto, Lynch et al. 2012). Volunteers in the jump group performed 10 jumping exercise per day at a frequency of 5 times a week for 2 weeks. Bone resorption measured by CTX was lower in the jump group compared to baseline. Additionally, TRAP5b was significantly lower in the jump group compared to the control group,

22-168 The Effect of Impact Loading on Bone Biomarkers in Energy-Restricted Female Runners

however, there was no significant changes in TRAP5b from baseline in either group. Interestingly, the jump intervention significantly lowered BAP, a marker of bone formation. No changes were observed in osteocalcin within or between groups. This study was limited based on lack of energy intake assessment and the potential for inter-subject variability in bone response to jumping exercises. Despite the theoretical basis for high-impact exercise as a countermeasure for bone resorption during LEA, there have been no controlled trials to date that have investigated this theory in energy-restricted athletes.

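### Can 12 completers detect only near-complete prevention of the P1NP fall under RUN?

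*Combined protocol and SAP*

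**What the plan says.** Section 14.1: "A power analysis determined that 12 women will be required to detect a clinically significant change of 10" µg/L in P1NP, with 80% power at P < 0.05. The basis is a cited study of low energy availability (LEA) during dietary restriction. Enrolment is set at 20 to allow for dropout. Section 14.3 adds: "We anticipate that we may need to screen between 50-60 participants to recruit and complete the required 12 participants". No SD, sidedness or baseline P1NP is given, nor whether the change is within a condition or between conditions.

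The hypothesis in section 2.2 is that adding jumps "will result in less suppression of bone formation following 5 days of endurance running in an energy-restricted condition", compared with running without them. It names no amount.

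Section 3.1 offers four pieces of evidence:
- In 8 male runners, P1NP and IGF-1 "decreased by 15% and 17%, respectively, after 3 consecutive days of treadmill running with energy intake restricted to 50% of estimated needs".
- In the 3-day study of 10 women, which appears to be the one section 14.1 cites: "In the combined diet and exercise LEA condition, participants received diets providing 30 kcal/kgFFM/d and expended 15 kcal/kgFFM/d during a treadmill run". There, "P1NP was significantly reduced after 3 days of LEA achieved through diet only, but not after the combined LEA condition with running".
- In the 5-day study, with the same intake and running expenditure in its low-EA condition: "In the female participants, P1NP was significantly lower after the low EA condition compared to optimal EA".
- In the jumping trial: "Interestingly, the jump intervention significantly lowered BAP, a marker of bone formation".

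Section 5.2 plans paired t-tests on the bone markers both within and between conditions.

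**The concern.** Less suppression is measured relative to what running alone does. Unless jumping lifts P1NP above baseline, the RUN+IL minus RUN difference cannot exceed the RUN fall. A target taken from a study of LEA itself could therefore equal the whole effect of LEA rather than the part jumping might prevent. If the RUN fall were about 10 µg/L, a trial sized for a 10 µg/L difference would be sized for complete prevention.

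The background seems to sharpen this. The only fall with a size is modest, the 3-day arm most like RUN showed no significant fall, and jumping lowered a formation marker in the one trial whose marker results are described. At stake is a null result that could mean three things: jumping does not help, RUN caused too little suppression to prevent, or too few women completed.

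**Working it through.** **Inputs.** From section 14.1: n = 12, δ = 10 µg/L, power 80%, α = 0.05. From section 5.2: paired t-test. From section 3.1: a 15% fall. Assumed, because the documents do not say: a two-sided test, δ read as RUN+IL minus RUN, and a range of baseline P1NP values.

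**Step 1: the plan's own figure.** Without an SD, 12 cannot be reproduced directly, so the SD of the paired difference (σ) is back-solved. Power is P(|T| > t₀.₉₇₅,ₙ₋₁), with T noncentral t on n − 1 degrees of freedom and noncentrality δ√n/σ. Setting power to 0.80 at δ = 10:
- n = 12 gives σ = 11.25
- n = 11 gives σ = 10.66

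Any SD between about 10.7 and 11.25 µg/L therefore rounds up to 12 women. The one-sided equivalent is 12.4 to 13.05. The stated requirement is coherent on this reading.

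**Step 2: power for smaller differences, σ = 11.25.**

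| Difference (µg/L) | Power, n = 12 | Power, n = 20 | Completers for 80% |
|---|---|---|---|
| 10 | 80% | 96% | 12 |
| 7.5 | 56% | 81% | 20 |
| 5 | 29% | 47% | 42 |

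The difference detectable with 80% power is 10.0 µg/L at 12 completers and 7.4 at 20. The 95% interval half-width at 12 is 2.201 × 11.25/√12 = 7.15, so a true difference of 5 gives an expected interval of about −2 to 12 µg/L.

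**Step 3: the ceiling.** A 15% fall equals 10 µg/L at a baseline of 10/0.15 = 66.7 µg/L. Both the size of the fall and the baseline move the answer.

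| Assumed fall | Baseline at which 10 µg/L is the whole fall |
|---|---|
| 10% | 100 |
| 15% | 66.7 |
| 20% | 50 |
| 30% | 33.3 |

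The share of the fall that 10 µg/L represents is 10/(fall × baseline):
- 15% fall: 111% at baseline 60, 83% at 80, 67% at 100
- 30% fall: 56% at 60, 42% at 80, 33% at 100

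The target thus runs from more than the whole fall to a third of it, depending on two quantities the documents do not give for women.

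**Step 4: which evidence applies to RUN.** The 15% comes from men over 3 days. Section 3.1 itself suggests that women may be more sensitive. The 3-day combined arm shares RUN's intake and expenditure, but a non-significant change in 10 women does not show that there was no fall. The 5-day study shares intake, running expenditure and duration with RUN, and found P1NP significantly lower in women. That comparison was with optimal EA, and no size is quoted. None of this fixes the RUN fall at 10 µg/L or less.

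**The case for a change.** The strongest reply is that the burden lies with section 14.1. Only RUN+IL versus RUN tests section 2.2. If 10 µg/L is instead a within-condition change, that contrast has no sample-size basis at all. Section 14.3 treats 12 as the requirement, the extra eight are for dropout, and section 15.4 says data from women who miss a condition cannot be used. Even 20 completers have only 47% power for 5 µg/L. A one-sided test does not rescue it: at σ = 13.05, power for 5 µg/L is 35% with 12 and 50% with 20. Even at a baseline of 100, halving a 15% fall gives 7.5 µg/L and 56% power at 12.

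Much of this stands. Section 14.1 is thin, and a modest benefit could well be missed. But half-prevention is the objection's choice of target, not the plan's. The plan claims 80% power for 10 µg/L and nothing for 5. If RUN lowers P1NP by 20 µg/L, half of it is 10 and 12 completers suffice. Nor is the ceiling absolute, because section 3.3 expects jumping to provoke an osteogenic response, so P1NP might rise above baseline. The jumping trial is weak contrary evidence: 10 jumps a day in non-athletes with no intake assessment, against 50 a day here.

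**Conclusion.** No change to the plan follows. The calculations are right, but near-complete prevention is not established. It needs a RUN fall of about 10 µg/L, for example 15% from a baseline near 67, and the documents support neither figure for women over 5 days.

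What remains falls into three parts:

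- **Missing detail.** Section 14.1 omits the contrast, the SD, the sidedness and the expected RUN fall. So 80% power for the section 2.2 contrast is not demonstrated, but it is not contradicted either: an SD of about 10.7 to 11.25 µg/L makes the stated figure hold.
- **A trade-off.** Sizing for a smaller share means more women. Requiring 20 completers would mean screening about 83 to 100 at the plan's own ratio (50/12 × 20 to 60/12 × 20), and 5 µg/L would need 42. Choosing that share needs figures from outside the documents. Enrolment of 20 already allows more than 12 to finish, with a detectable difference of 7.4 µg/L if all do.
- **Interpretation of a null.** Section 5.2 already tests the RUN change and the between-condition difference. An analyst would read the two together, with intervals from the same paired data. Making the contrast conditional on a demonstrated RUN fall is debatable and offers no clear gain.

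The power figures assume a two-sided paired t-test, δ read as RUN+IL minus RUN, and the back-solved SD of 11.25 µg/L. A different SD would change them.
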